CRYSTALSIGHT: Clinical Evaluation of OCCUTRACK's CRYSTALSIGHT Device through Remote Monitoring for Disease Recurrence of Wet AMD (Cohort 2.0)

Main Study Site: Tan Tock Seng Hospital, Singapore

Principal Investigator:

[name]

Senior Consultant
NHG Eye Institute,
Tan Tock Seng Hospital
National Healthcare Group, Singapore

Co-Investigator(s):

[name] [name]

Senior Resident
NHG Eye Institute,
Tan Tock Seng Hospital
National Healthcare Group, Singapore

Collaborators:

[name] [name]

Clinical Research Coordinator
NHG Eye Institute,
Tan Tock Seng Hospital
National Healthcare Group, Singapore

[name]

Chief Executive Officer
OCCUTRACK Medical Solutions Pte Ltd

Study Summary

Age-Related Macular Degeneration (AMD) and Diabetic macular Edema (DME) is one of the main causes of central vision loss. Most patients require pharmacologic treatment with anti-vascular endothelial growth factor (VEGF) agents with multiple follow-up visits that include optical coherence tomography (OCT), visual acuity testing and multiple injections.

The high frequency of visits puts pressure on eye clinics and can be extremely stressful for both patients and their caregivers. Therefore, portable and rapidly deployable self-administered home-based examination devices are key to making telemedicine a reality.

OCCUTRACK Medical Solutions has developed a portable, self-administered device designed for gaze-tracking and monitoring of patients with retinal diseases such as

OCCUTRACK

AMD and DME, and choroidal neovascularization (CNV) that require multiple anti-VEGF injections.

The team have confirmed the performance of the CRYSTALSIGHT device and validated the retinal thickness measurements obtained with this device by comparing it to in-hospital Optical Coherence Tomography (OCT) (Heidelberg Spectralis). In this study, the team will conduct a randomized clinical trial RCT to compare the efficacy and cost-effectiveness of a Pro Re Nana (PRN) management regimen enhanced with the CRYSTALSIGHT home monitoring device for the detection of central metamorphopsia with existing PRN standard of care for patients with AMD or DME exiting the anti-VEGF injection regimen.

Study Objectives

Primary Objective:

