To demonstrate that the home monitoring of a PRN regimen with the CRYSTALSIGHT telemonitoring system is non-inferior to the Amsler grid¹ in detecting recurrence of wet AMD based on central retinal thickness (CRT) increase of at least 50 microns or a loss of best-corrected visual acuity (BCVA) of 5 letters or more.

Detection of using visual field test gaze tracking results in earlier detection of AMD/DME associated with (CNV), as reflected by better visual acuity compared with standard care. Outcome of this trial is to determine the sensitivity and specificity of CRYSTALSIGHT with reactivation subtle neovascular age-related macular degeneration that was detected by the regular use of a home monitoring device based on gaze-based preferential hyperacuity visual field testing.

An important predictor of the benefit of treatment with anti-vascular endothelial growth factor (VEGF) agents is visual acuity at the time of CNV treatment.

Secondary Objectives

1. Correlate CRYSTALSIGHT scores with BCVA and OCT findings.
2. Identify diagnostic performance of CRYSTALSIGHT (ROC, AUC).
3. Develop risk scoring algorithms for wet AMD recurrence.

Background work

For patients who have lost vision in one eye due to wet age-related macular degeneration (wAMD), preservation of functional visual acuity in the other eye is of paramount importance. However, clinical experience and research have shown that these and other high-risk patients often fail to use the Amsler grid between clinic visits to detect the earliest signs of neovascularization in their good eye.

Normal human vision consists of a series of rapid eye movements called saccades that abruptly change the fixation point depending on the area of the person's eye. OCCUTRACK's CRYSTALSIGHT device tracks these eye movements with generated

OCCUTRACK

patterns on the screen, a visual assessment of affected and unaffected eyes is achieved without expensive optics and at home on any tablet or laptop computer.

CRYSTALSIGHT is a home-based gaze-tracking readily available for home hyperacuity monitoring for these and other high-risk eyes with diagnosed wet-AMD.

The Device

[figure not shown]

Figure 1 CRYSTALSIGHT device being used in a home-based setting.

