The Cohort 2 study typically several phases, including a screening phase to identify eligible patients who could be recruited patients exiting the anti-VEGF injection clinic. The phases are:

- **Training:** a training phase for the device to ensure that patients know how to use the device properly, a testing phase in which patients use the device to monitor their vision condition using the CRYSTALSIGHT device over a period of time until the device detects deterioration in vision and meets the criteria for deterioration established by the Cohort 1 results, and a follow-up phase to assess results and obtain feedback from patients.
- **Monitoring:** During the study, patients will be asked to follow the specific protocols and guidelines for use of the CRYSTALSIGHT device, such as completing the bi-weekly regular testing. Patients will also be asked to report or provide feedback on any adverse events or problems encountered while using the device.
- **Intervention:** Should the CRYSTALSIGHT device determine that a threshold for vision deterioration has been reached (delta deviation of 10 points from the nominal baseline), the patient/participant will receive a notification from the prescribing physician and the electronic alert system via email to the subject's personal mobile device instructing them to schedule an appointment for confirmation OCT -A that the subject's wet AMD has recurred, see Figure 6 below.

[figure not shown]

Figure 6 True-False confusion matrix of cohort-2 will require OCT confirmation of wet AMD disease recurrence that was detected by CRYSTALSIGHT.

This cohort 2 intervention study is designed to collect data on the safety and efficacy of the device, including information on the accuracy, reliability, and ease of use of the device. The study may also examine the impact of the device on patient outcomes, such as changes in visual status or quality of life.

Once the study is complete, the data will be analyzed to determine if the device is safe and effective for home use. If the results are positive, the device can be submitted to the FDA for approval and made available to patients who need it.

OCCUTRACK

Cohort-2 study relationship to the cohort-1

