The CRYSTALSIGHT eye tracking system is a medical monitoring system used to treat age-related macular degeneration (AMD). AMD is a disease that affects the macula, the part of the eye responsible for central vision. CRYSTALSIGHT helps people with AMD maintain their quality of life by improving their ability to perform everyday activities.

[figure not shown]

Figure 7 Cohort 1 results of a single test subject showing the correlation of OCT scores to CRYSTALSIGHT at two clinic visits.

[figure not shown]

Figure 8 Population of cohort-1 study, each box represents a tested eye (total 36 eyes in this plot), each dot represents a single clinic visit, green = CRYSTALSIGHT, blue = OCT.

OCCUTRACK

	Cohort 1	Cohort 2
Trial objectives	Verify OCT versus CRYSTALSIGHT correlation (threshold score)	wAMD/DME recurrence detection - (intervention alerts)
Device	CRYSTALSIGHT camera with Tobii ET5L	CRYSTALSIGHT camera only OR Digitized amsler Grid
Physician interaction	Four times: 1. Registration 2. First follow up 3. 2 nd follow up 4. Exit	PRN* regimen: 1. Registration 2. Monthly clinic visits 3. Intervention 4. Exit *(PRN scheduled clinic visits will proceed normally)
Size	100	220
Intended use	Clinic based	Home-based

In Cohort-1, the CRYSTALSIGHT system will be used in a clinical setting under the guidance of a trained healthcare professional to confirm the correlation between CRYSTALSIGHT and OCT in the same study participant longitudinally and establish a threshold for "deterioration."

Recruitment

- Eligibility Diagnosis:** The PI determine eligibility and will inform a potential participant (diagnosed with wAMD who is on a treatment regimen) to determine if CRYSTALSIGHT is an appropriate monitoring option.
- Enrolment:** If CRYSTALSIGHT is deemed appropriate for the patient, the PI or study coordinator will enroll the patient in the trial for the device and provide the patient with instructions for using the device.
- Training:** the study coordinator trains the participant on a CRYSTALSIGHT device to familiarise the patient with the device and ensures that the patient understands and follows the rules for home use.
- Initial monitoring:** The PI will start the participant on self-monitoring with CRYSTALSIGHT twice a week and monitor the participant's baseline gaze performance via the CRYSTALSIGHT electronic database.

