5. Subjects undergoing treatment for Wet-AMD without any signs and symptoms of recurrence of active AMD (AMD recurrence: choroidal neovascularisation,

OCCUTRACK

intraretinal or subretinal fluid is present) with OCT lesion fluid volume more than 2 mm² or ILM height more than 300µm.

6. Ability to comply with the study protocol, in the investigator's judgment.
7. Subjects must be able to understand and provide informed consent. A signed informed consent form must be provided before any study assessments.

Exclusion criteria

1. Unable to understand verbal spoken instructions and demonstrate device functionality and implementation.
2. Unable to turn on and connect the CRYSTALSIGHT device to a computer independently.
3. Any ocular surgery in the previous 3 months, or vitrectomy in the previous 12 months
4. Any history of macular pathology unrelated to AMD affecting vision or contributing to the presence of intraretinal or subretinal fluid in the study eye
5. Any concurrent intraocular condition in the study eye that, in the opinion of the investigator, could either reduce the potential for visual improvement or require medical or surgical intervention during the study
6. Any prior or concomitant treatment for CNV or vitreomacular-interface abnormalities in the study eye.
7. History of idiopathic or autoimmune-associated uveitis in either eye
8. Active ocular inflammation or suspected or active ocular or periocular infection in either eye.

Study population: patients with recurrent vision problems diagnosed with active Wet-AMD at TTSH eye clinics.

Pre-specified clinical outcome: The prespecified adverse clinical outcome used in this study will be the **recurrence of Active Wet AMD**, which will be identified by an increase in central retinal thickness (CRT) of at least 50 microns or a loss of best-corrected VA of 5 letters or more.

Training

To prepare for home use of the CRYSTALSIGHT device, the following processes are performed in the clinic:

- The examining physician or study coordinator will unpack a CRYSTALSIGHT training unit for the patient to help the patient understand the device and ensure that the home user understands the device, its purpose, and how it works. Instructions on how to set it up at home include connecting the device to a laptop with an Internet connection.

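### Exclusion 6 bars every study eye already treated for wet AMD, contradicting inclusion 5, the recruitment text and the recurrence objective

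*Protocol*

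**What the plan says.** **The exclusion.** Under Eligibility, exclusion 6 removes a participant for "Any prior or concomitant treatment for CNV or vitreomacular-interface abnormalities in the study eye". It names no agent, period or exempt treatment, and nothing elsewhere in the Protocol narrows it.

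**The inclusion.** Inclusion 5, in the same section, calls for "Subjects undergoing treatment for Wet-AMD without any signs and symptoms of recurrence of active AMD". Its bracketed definition of recurrence begins "AMD recurrence: choroidal neovascularisation".

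**The source population.**
- The Study Summary compares regimens for "patients with AMD or DME exiting the anti-VEGF injection regimen".
- The description of study phases under Study Design speaks of "recruited patients exiting the anti-VEGF injection clinic".
- The Recruitment section describes a candidate as "diagnosed with wAMD who is on a treatment regimen".

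**The target event.** The Primary Objective and the Pre-specified clinical outcome are both recurrence of wet AMD. The Methodology section words the target as recurrence of the CNV that accompanies wet AMD.

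**The study eye.** The Protocol does not say which eye it is. The device-arm section (PRN+) allows for a field defect in one or more study eyes of a participant, so more than one study eye per person is possible.

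**The concern.** A trial of recurrence needs eyes that have had the disease and, in this setting, have been treated for it. Exclusion 6 removes those eyes. Sites then have two courses, and neither is sound:

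- **Apply it as written.** The trial loses the eyes in which recurrence is to be detected. What remains is untreated study eyes, where an event would be a first CNV. That is a different question from the one in the primary objective.
- **Set it aside.** Every treated study eye enrolled is then a breach of a stated eligibility criterion.

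Three sites in three countries are planned, and the Protocol gives them no rule for choosing between these courses.

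The criteria apply before randomisation and to both arms, so this is not a source of bias between arms. The fault is that the criteria, taken together, do not describe the population in the primary objective.

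**Working it through.** The plan states no figure on this point, so there is nothing to reproduce. The check sets the passages side by side and then works through the possible cases.

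**Step 1. Is treatment for wet AMD the same as treatment for CNV in this Protocol?** Three places say it is:
- The Methodology section makes recurrence of CNV associated with wet AMD the thing to be detected.
- Inclusion 5 names CNV in its own definition of AMD recurrence.
- The Primary Objective section uses the term for anti-VEGF treatment: "An important predictor of the benefit of treatment with anti-vascular endothelial growth factor (VEGF) agents is visual acuity at the time of CNV treatment".

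A study eye treated for wet AMD has therefore been treated for CNV, and exclusion 6 applies to it.

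**Step 2. Which patients pass both criteria?** Inclusion 5 is written per subject: it is met if either eye is under treatment. Exclusion 6 is written per study eye. With one study eye per participant:

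| Study eye treated | Fellow eye treated | Inclusion 5 | Exclusion 6 | Eligible |
|---|---|---|---|---|
| yes | yes | met | triggered | no |
| yes | no | met | triggered | no |
| no | yes | met | not triggered | yes |
| no | no | not met | not triggered | no |

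Neither of the 2 cases with a treated study eye is eligible. Of all 4 cases, 1 is eligible: treatment in the fellow eye only.

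**Step 3. What if both eyes are study eyes?** Exclusion 6 is then triggered whenever either eye has been treated, which is exactly when inclusion 5 is met. None of the 4 cases is eligible: 3 fail exclusion 6, and the case with neither eye treated fails inclusion 5.

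**Step 4. How many breaches if exclusion 6 is not applied?** Let f be the share of the 220 planned participants with a treated study eye. The Protocol does not give f, so the values below are assumptions. Breaches = 220 × f:
- f = 0.25: 220 × 0.25 = 55
- f = 0.5: 220 × 0.5 = 110
- f = 1: 220 × 1 = 220

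**Step 5. The concomitant limb.** The Study Schedule Table lists intravitreal injection at baseline without marking it optional, and as optional at most later visits. The Sample size calculation section also foresees injections during the study. These passages do not name the eye, so they add to the tension but do not settle it.

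**Minor item.** Inclusion 4 accepts a person who connects the device with family help. Exclusion 2 removes anyone who cannot do so alone. A family-assisted user meets the first and is barred by the second. The number of such users is not given.

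**The case against.** **The fellow-eye reading.** Because inclusion 5 is per subject and exclusion 6 per study eye, a patient treated only in the other eye satisfies both. Some text favours this reading. The Background work section is concerned with patients who have lost vision in one eye and need to "detect the earliest signs of neovascularization in their good eye", and Study Design refers to progression to CNV. The logic stands: the two criteria are not strictly incompatible for every patient. It does not rescue the plan. An untreated study eye does not fit a primary objective, methodology and outcome all written as recurrence. The same Background section presents the device for eyes already diagnosed with wet AMD. Exclusion 4 bars only macular disease unrelated to AMD, which presupposes that AMD in the study eye is acceptable.

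**A separate meaning of CNV.** The Study Summary lists CNV beside AMD and DME as if it were a distinct indication, so exclusion 6 might be aimed at something else. Step 1 shows the Protocol's other uses go against this, and nothing states the narrower meaning. At best the wording is ambiguous, which is still a defect in an eligibility criterion.

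**The two-study-eye case is thin.** This is fair. It rests on one phrase in the device-arm section, and the Protocol never says that both eyes are enrolled. The finding does not depend on it.

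**The numbers add little.** Also fair. The case counts carry no frequencies, and 220 × f only restates the assumed f. They show the range of possible breaches and are not evidence for the conflict.

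**The intent is obvious and sites will ask.** They may well. Error rates, margin and sample size are untouched. But the text offers no answer when they do.

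**Conclusion.** The concern holds and must be fixed. As written, exclusion 6 makes every study eye already treated for wet AMD ineligible. That contradicts inclusion 5 as applied to such an eye, the recruitment text, and the recurrence objective and outcome. The only route through both criteria is treatment confined to the fellow eye, which changes the event from a recurrence to a first CNV.

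The conclusion rests on the wording and on the Protocol's own use of CNV for the wet-AMD lesion; it needs no numerical assumption. The possible number of breaches runs from 55 to 220 of 220 for assumed shares of 0.25 to 1, and the true share is not in the document.

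The conflict between inclusion 4 and exclusion 2 is real but minor and carries no weight in this grading.

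**What to change.** Reconcile exclusion 6 with inclusion 5, the recruitment statements (Study Summary, Study Design phases, Recruitment) and the recurrence objective and outcome, so that the written criteria admit the eyes in which recurrence is to be detected. State which eye is the study eye, or that both are. What scope of CNV treatment, if any, stays excluded is for the sponsor and investigators to decide.

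In the same amendment, make inclusion 4 and exclusion 2 state one rule on family-assisted set-up, whichever is intended.

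The cost is a protocol wording amendment, with no added patients or procedures. The Protocol gives an estimated start of June 2025 but no enrolment status. If enrolment has begun, the eligibility of participants already in the trial would need to be re-documented against the amended wording.

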A single large discrete target is displayed filling the entirety of the screen and shrinks to 10pixels for 5 seconds. The target is presented twice. The user under test's fixation radius is scored as a Circular-Error Probable (CEP) size. The smaller the CEP radius, the better the test result.	A set of 13 discrete targets are displayed randomly and twice repeatedly on fixed coordinates for a preset duration of 1 second (adjustable) on the screen for the user under test. Targets are presented in a pseudo-randomly to avoid bias in gaze point detection. An area-of-effect radius is scored if the user's gaze intersects with the presented target.	A set of 13 discrete targets that increases in radius at 10 pixels/second are displayed randomly on fixed coordinates on the screen for the user under test. Targets are presented in a pseudo-randomly to avoid bias in gaze point detection. The target radius is scored if the user's gaze intersects with the presented target at the presented radius size. The smaller the radius, the better the test result.	Subject under test to pursue a generated target moving in a sinusoidal pattern at a speed of 5cm/s.

OCCUTRACK

Methodology

This study aims to determine whether home-based monitoring using the CRYSTALSIGHT gaze-based Hyperacuity Perimetry system, when added to a PRN treatment regimen, is non-inferior to standard care using the Amsler Grid in detecting recurrence of choroidal neovascularisation (CNV) associated with wet age-related macular degeneration (AMD).

Recurrence is defined by a central retinal thickness (CRT) increase of ≥ 50 microns or a loss of best-corrected visual acuity (BCVA) of ≥ 5 letters.

The study also aims to evaluate whether CRYSTALSIGHT enables earlier detection of CNV progression, as reflected by better VA and CRT values at the time of detection, through biweekly self-tests conducted in an unsupervised home setting.

Study Design

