This is a randomised, open-label, non-inferiority clinical trial comparing two parallel arms: a standard care arm using Amsler Grid home monitoring (PRN), and an intervention arm using the CRYSTALSIGHT gaze-tracking system (PRN+). A total of 220 (Singapore – 60, United Kingdom – 80, United States – 80) participants will be randomised in a 1:1 ratio. Participants in the intervention arm will self-administer biweekly CRYSTALSIGHT tests at home, while those in the control arm will use the Amsler Grid. Both arms will attend monthly clinic visits for standard evaluations, including VA, BCVA, and OCT. Alerts generated by the CRYSTALSIGHT system based on deviation thresholds will trigger early clinic recall for confirmatory imaging and potential re-treatment.

[figure not shown]

Figure 4 Details of the home-use clinical trial study design. The trial objective: show that PRN+ is non-inferior to standard of care PRN with better VA/VF outcomes

Development of CRYSTALSIGHT cutoff scores should have been conducted in the cohort-1 1 study [NCT: NCT06518512] (Analysis). This Phase 2 should be the application of validated cut-off scores. The second aim will be to compare the accuracy of CRYSTALSIGHT and Amsler, and sensitivity and specificity check.

In addition to identifying CRYSTALSIGHT visual risk prediction cut-off scores, detection yields, and diagnostic Performance indicators will also be evaluated. Progression to CNV was

OCCUTRACK

determined by the investigator, based on standardised OCT confirmation. At the clinical trial site, these events were confirmed by gradings conducted by masked, certified independent personnel who did not know the treatment assignment. Events from both arms are graded using a standardised protocol.

[figure not shown]

Figure 5 In Cohort 2, home-based score deviation detected, study coordinator will schedule hospital checkup immediately. If CRYSTALSIGHT correctly detects wet AMD recurrence confirmed by OCT, subject exits the study.

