For participants in the CRYSTALSIGHT group, each participant will have a testing result by CRYSTALSIGHT and by OCT every 4 weeks or less if the positive result triggers a clinical visit. The result is considered correct if it is consistent with the findings of the OCT scan. During the one-year study period, the total number of correct results generated by CRYSTALSIGHT will be counted and the accuracy for these participants will be calculated as number of correct results divided by the total number of clinical visit. For participants in the Amsler Grid group, the accuracy for each participant will also be calculated.

According to literature, the accuracy of Amsler Grid in detecting disease activity was about 80%, we will assume that CRYSTALSIGHT has the same accuracy. For the Singapore population, we will also assume that standard deviation of the accuracy to be 0.12 and setting the maximum allowable difference in accuracy (non-inferiority margin) between the two groups to be 0.09, with one-sided type 1 error of 0.025 and a power of 0.8, a total of 52 participants will be required (26 per group). Considering of 15% attrition rate, a total of 60 participants will be required.

For global study, we assume a higher standard deviation of the accuracy to be 0.21 and a dropout rate of 21%, a total of 220 participants will be required (110 per group).

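### The stated objective is non-inferiority in detecting recurrence, but the 0.09 margin and N = 220 apply to agreement with OCT over all visits

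*Protocol*

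**What the plan says.** The Primary Objective is to show that CRYSTALSIGHT home monitoring is non-inferior to the Amsler grid "in detecting recurrence of wet AMD based on central retinal thickness (CRT) increase of at least 50 microns", or a BCVA loss of 5 letters or more. Methodology repeats this aim for recurrent CNV and gives the same two-part definition, the second part being "a loss of best-corrected visual acuity (BCVA) of ≥ 5 letters".

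The Sample size calculation section defines another quantity. For each test result, "The result is considered correct if it is consistent with the findings of the OCT scan". Then "the accuracy for these participants will be calculated as number of correct results divided by the total number of clinical visit", and the Amsler arm is scored in the same way. Both arms are assumed to have 80% accuracy. The margin is fixed by "setting the maximum allowable difference in accuracy (non-inferiority margin) between the two groups to be 0.09", with one-sided type 1 error 0.025 and power 0.8. The global calculation changes the standard deviation to 0.21 and dropout to 21%, and arrives at 220.

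Sensitivity and specificity also appear. The Primary Objective section says "Outcome of this trial is to determine the sensitivity and specificity of CRYSTALSIGHT", and Study Design says "The second aim will be to compare the accuracy of CRYSTALSIGHT and Amsler, and sensitivity and specificity check". ROC and AUC are a secondary objective. Detection yields and a confusion matrix against OCT are also mentioned. None of these has a margin or success criterion in the protocol.

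**The concern.** The claim and the quantity tested differ in two ways.

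- Accuracy over all visits mixes sensitivity and specificity, weighted by how often OCT is positive. If most visits are OCT-negative, a test scores well mainly by staying silent, and a large loss of sensitivity moves accuracy only slightly.
- A result is scored against the OCT scan alone. A recurrence that meets the definition through BCVA loss only does not count as one in the accuracy measure.

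At stake is what a positive trial may conclude. Meeting the 0.09 margin supports non-inferiority in overall agreement with OCT. It does not by itself support non-inferiority in detecting recurrence, which is what the objective states.

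**Working it through.** **Inputs from the protocol (Sample size calculation):** margin 0.09; accuracy 0.80 in both arms; SD 0.21 (taken for both arms); one-sided 0.025; power 0.80; dropout 21%; N = 220. The margin appears in the Singapore sentence and is not restated for the global study.

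**Assumed, because the protocol gives no figure:** p, the share of OCT-positive visits, shown from 0.10 to 0.50 and first taken as equal in both arms.

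**1. Does 220 rest on the accuracy margin?**
n per arm = 2 × ((1.96 + 0.8416) × 0.21 / 0.09)² = 85.5, so 86. Total 172; 172 / 0.79 = 218, against 220 stated. It does, with the 0.09 margin carried over to the global study.

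**2. What the margin means for sensitivity.**
Mean accuracy = p × Se + (1 − p) × Sp. With equal specificity and a sensitivity deficit d, the difference in accuracy is D = −p × d. The deficit lying exactly on the margin is d = 0.09 / p.

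**3. Chance of declaring non-inferiority.**
SE = 0.21 × √(2/86) = 0.0320. P = Φ((0.09 + D) / 0.0320 − 1.96).

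- Device with sensitivity 0.30 below the Amsler grid and equal specificity: D = −0.30p.
- Limiting case, a device that never alerts: its accuracy is 1 − p, so against the protocol's 0.80 control accuracy D = 0.20 − p.

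| p | Deficit at the margin, 0.09/p | P, device 0.30 less sensitive | P, never-alerting device |
|---|---|---|---|
| 0.10 | 0.90 | 0.47 | >0.99 |
| 0.20 | 0.45 | 0.15 | 0.80 |
| 0.30 | 0.30 | 0.025 | 0.01 |
| 0.50 | 0.18 | <0.001 | <0.001 |

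**4. Effect of the exit rule.** The Figure 5 caption says that a device-arm participant leaves the study after an OCT-confirmed detection. Whether control participants also leave is not stated. I simulated 12 visits with independent recurrences at a per-visit rate of 0.10, specificity 0.85 in both arms, and sensitivity 0.40 (device) against 0.70 (Amsler). Without exit, D = 0.10 × (0.40 − 0.70) = −0.030. With exit in the device arm only, D is about −0.016. The gap roughly halves because each departing participant's record ends on a correct result. With exit in both arms, the same set-up gives no such shrinkage.

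**5. Precision available for sensitivity itself.** With m first recurrences per arm and sensitivity 0.7 in both arms, the 95% half-width for the difference is 1.96 × √(2 × 0.7 × 0.3 / m) = 1.96 × √(0.42 / m). This gives ±0.14 for m = 86, ±0.19 for m = 43 and ±0.28 for m = 20.

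**The case against.** The strongest reply is that this is a choice of metric. The Sample size calculation section introduces accuracy as accuracy in detecting disease activity, so the protocol arguably uses it to make detection measurable, and accuracy is a legitimate diagnostic endpoint. That holds for a claim about agreement with OCT. It does not show that the 0.09 margin limits lost detection, and the protocol never discusses the weight given to true negatives.

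A second reply is that sensitivity, specificity, ROC/AUC, detection yields and a confusion matrix are all planned. This stands in part. A reader might infer that a poor detector could pass unnoticed, and the documents do not support that, because these results would show it. But most of them concern CRYSTALSIGHT alone, and none has a success criterion in the protocol. A SAP may set one; N would still have been sized for accuracy.

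A third reply is that the size rests on p, and this stands. A reader might infer that OCT-positive visits are rare, so that the margin gives almost no protection. The text does not settle it. Entry without signs of recurrence, scans every 4 weeks and exit after detection point to a low p. The study population, however, is described as having active wet AMD.

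Finally, the formula assumes equal p in both arms and a fixed set of visits, whereas the plan averages within participants and allows extra alert-triggered visits. The table is therefore an illustration and not a property of this trial.

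**Conclusion.** The mismatch is certain from the protocol's own text: the objective concerns detecting recurrence by thickness or BCVA, while the only margin and the sample size concern agreement with OCT over all visits. Its size is conditional. With equal specificity and equal p, the margin equals a sensitivity deficit of 0.09/p, which is severe at p = 0.10, still large at 0.20, and fades as p rises. Exit after detection in the device arm only would make it worse.

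It would go too far to say that a non-alerting device will pass. Against the protocol's 0.80 control accuracy, that probability runs from above 0.99 at p = 0.10 to 0.01 at p = 0.30. Nor do the documents establish that a visit-level sensitivity comparison is biased; it may be, if exit differs by arm. This should be fixed; confidence in its size is moderate, because p is unknown.

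**What to change.** In the objective and sample-size sections, state:

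- that meeting the 0.09 margin supports only non-inferiority in overall agreement with OCT;
- that the 80% power of N = 220 is for that quantity only;
- the share of OCT-positive visits that is assumed.

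Base any statement about detecting recurrence on sensitivity and specificity by arm, with confidence intervals. Take sensitivity per participant at first recurrence as the protocol defines it (thickness or BCVA). Take specificity over visits before first recurrence, with intervals clustered by participant. This avoids a visit-level comparison that differing exit could distort.

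The cost is text in two sections, with no added participants or visits. The headline claim becomes narrower, and the interval for the sensitivity difference will be wide: about ±0.14 with 86 recurrences per arm and ±0.28 with 20, at sensitivity 0.7.

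A separate point needs reconciling: Study Design includes BCVA at monthly visits, while the Study Schedule Table marks it as optional.
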